## 8. SAFETY MONITORING AND REPORTING

### 8.1 Adverse Events

#### 8.1.1 Definitions and Reporting

An AE is defined as the appearance of (or worsening of any pre-existing) undesirable sign(s), symptom(s), or medical condition(s) that occur after subject's signed informed consent has been obtained.

Adverse events that begin or worsen after informed consent should be recorded in the AEs CRF. Conditions that were already present at the time of informed consent should be recorded in the Medical History CRF. Adverse event monitoring should be continued for 28 days following the last dose of study treatment. Adverse events (including lab abnormalities that constitute AEs) should be described using a diagnosis whenever possible, rather than individual underlying signs and symptoms. When a clear diagnosis cannot be identified, each sign or symptom should be reported as a separate AE.

Subjects will be instructed to report AEs during the study and staff will query subjects regarding AEs throughout the study. The investigator (and/or designee) must document all AEs reported by the subject from the time subjects give consent through completion of the EOS visit. Any subject who is withdrawn from the study due to an AE shall be followed until the event has resolved or stabilized or 28 days after last dose and the investigator will document available follow-up information on the subject's source documentation and CRF.

Adverse events reported after consent but before the first dose of study treatment are still to be documented by the investigator but will be considered non-treatment-emergent AEs. Adverse events will be considered treatment emergent if the onset date is after the first dose of study drug.

All AEs and SAEs will be assessed for severity using the Division of AIDS (DAIDS) Table for Grading the Severity of Adult and Pediatric Adverse Events, version 2.1 (July 2017).

For AEs not included in the Table, the following guidelines will be used to describe severity. In addition, all deaths related to an AE are to be classified as grade 5 according to the DAIDS Table.

**Mild:** Mild symptoms causing no or minimal interference with usual social and functional activities, with intervention not indicated.

**Moderate:** Moderate symptoms causing greater than minimal interference with usual social and functional activities, with intervention indicated.

**Severe:** Severe symptoms causing inability to perform usual social and functional activities, with intervention or hospitalization indicated.

**Potentially life-threatening:** Potentially life-threatening symptoms causing inability to perform basic self-care functions with intervention indicated to prevent permanent impairment, persistent disability, or death.

An event is defined as 'serious' when it meets at least 1 of the predefined outcomes as described in the definition of an SAE, NOT when it is rated as severe.

“Lack of efficacy” or “failure of expected pharmacological action” per se will not be reported as an AE or SAE. Such instances will be captured in the efficacy assessments. However, the signs, symptoms, and/or clinical sequelae resulting from lack of efficacy will be reported as AE or SAE if they fulfill the definition of an AE or SAE.

### **8.1.2 Events NOT Meeting the AE Definition:**

- The following study-specific clinical events related to COVID-19 are exempt from AE reporting unless the investigator deems the event to be related to the administration of study drug:
  - Hypoxemia due to COVID-19 requiring supplemental oxygen;
  - Hypoxemia due to COVID-19 requiring non-invasive ventilation or high flow oxygen devices;
  - Respiratory failure due to COVID-19 requiring invasive mechanical ventilation or ECMO.
- Any clinically significant abnormal laboratory findings or other abnormal safety assessments which are associated with the underlying disease, unless judged by the investigator to be more severe than expected for the subject’s condition.
- The disease/disorder being studied or expected progression, signs, or symptoms of the disease/disorder being studied, unless more severe than expected for the subject’s condition.
- Medical or surgical procedure (e.g., endoscopy, appendectomy): the condition that leads to the procedure is the AE.
- Situations in which an untoward medical occurrence did not occur (social and/or convenience admission to a hospital).
- Anticipated day-to-day fluctuations of pre-existing disease(s) or condition(s) present or detected at the start of the study that do not worsen.

### **Classification of AEs by Relationship to Study Drug**

**UNRELATED:** This category applies to those AEs that are clearly and incontrovertibly due to extraneous causes (disease, environment, etc.).

**UNLIKELY:** This category applies to those AEs that are judged to be unrelated to the test drug, but for which no extraneous cause may be found. An AE may be considered unlikely to be related to study drug if or when it meets 2 of the following criteria: (1) it does not follow a reasonable temporal sequence from administration of the test drug; (2) it could readily have been produced by the subject’s clinical state, environmental or toxic factors, or other modes of therapy administered to the subject; (3) it does not follow a known pattern of response to the test drug; or (4) it does not reappear or worsen when the drug is re-administered.

**POSSIBLY:** This category applies to those AEs for which a connection with the test drug administration appears unlikely but cannot be ruled out with certainty. An AE may be

considered possibly related if or when it meets 2 of the following criteria: (1) it follows a reasonable temporal sequence from administration of the drug; (2) it could not readily have been produced by the subject's clinical state, environmental or toxic factors, or other modes of therapy administered to the subject; or (3) it follows a known pattern of response to the test drug.

**PROBABLY:** This category applies to those AEs that the investigator feels with a high degree of certainty are related to the test drug. An AE may be considered probably related if or when it meets 3 of the following criteria: (1) it follows a reasonable temporal sequence from administration of the drug; (2) it could not be reasonably explained by the known characteristics of the subject's clinical state, environmental or toxic factors, or other modes of therapy administered to the subject; (3) it disappears or decreases on cessation or reduction in dose (note that there are exceptions when an AE does not disappear upon discontinuation of the drug, yet drug-relatedness clearly exists; for example, as in bone marrow depression, fixed drug eruptions, or tardive dyskinesia); or (4) it follows a known pattern of response to the test drug.

**DEFINITELY:** This category applies to those AEs that the investigator feels are incontrovertibly related to test drug. An AE may be assigned an attribution of definitely related if or when it meets all of the following criteria: (1) it follows a reasonable temporal sequence from administration of the drug; (2) it could not be reasonably explained by the known characteristics of the subject's clinical state, environmental or toxic factors, or other modes of therapy administered to the subject; (3) it disappears or decreases on cessation or reduction in dose and recurs with re-exposure to drug (if rechallenge occurs); and (4) it follows a known pattern of response to the test drug.

All AEs (regardless of seriousness or relationship to study drug) including those from the time of consent to the EOS visit are to be recorded in the subject's source documents and on the corresponding page(s) in the CRF. The investigator should specify the date of onset, intensity, action taken with respect to study drug, corrective treatment/therapy given, outcome and his/her opinion as to whether there is a reasonable possibility that the AE was caused by the study drug. All medications administered to treat an AE must be recorded in the subject's source documentation and reported in the CRF.

### 8.1.3 Laboratory Test Abnormalities

Laboratory abnormalities that constitute an AE in their own right (are considered clinically significant, induce clinical signs or symptoms, require concomitant therapy, or require changes in study treatment), should be recorded on the AEs CRF.

Whenever possible, a diagnosis, rather than a symptom should be provided (e.g. anemia instead of low hemoglobin). Laboratory abnormalities that meet the criteria for AEs should be followed until they have returned to normal or an adequate explanation of the abnormality is found. When an abnormal laboratory or test result corresponds to a sign/symptom of an already reported AE, it is not necessary to separately record the lab/test result as an additional event.

Laboratory abnormalities, that do not meet the definition of an AE, should not be reported as AEs.

## **8.2 Adverse Events of Special Interest (AESI)**

The Adverse events of special interest (AESI) search table will be used to map reported AEs to the notable AE groupings. AESI could be updated during the course of study based on accumulating safety data. Therefore the clinical study report includes the AE groupings (such as gastrointestinal disorders, cardiovascular disorders, increased liver transaminase, and neurological disorders, peripheral blood cytopenia and renal disorders). used and provide a listing of the corresponding AESI search table. AESI will be summarized regardless of study drug relationship, by grouping, PT and treatment arm.

## **8.3 Serious Adverse Events**

### **8.3.1 Definitions**

If an event is not an AE per definition above, then it cannot be an SAE even if serious conditions are met (e.g., hospitalization for signs/symptoms of the disease under study, death due to progression of disease).

An SAE is defined as one of the following:

- Is fatal
- Is life-threatening
- Results inpatient hospitalization or prolongation of existing hospitalization
- Results in a persistent or significant disability/incapacity
- Constitutes a congenital anomaly/birth defect
- Is medically significant, i.e., defined as an event that jeopardizes the patient or may require medical or surgical intervention to prevent one of the outcomes listed above
- Note that hospitalizations for the following reasons should not be reported as SAEs:
  - a. Routine treatment or monitoring of the studied indication, not associated with any deterioration in condition.
  - b. Elective or pre-planned treatment for a pre-existing condition that is unrelated to the indication under study and has not worsened since signing the informed consent.
  - c. Social reasons and respite care in the absence of any deterioration in the patient's general condition.
- Note that treatment on an emergency outpatient basis that does not result in hospital admission and involves an event not fulfilling any of the definitions of a SAE given above is not an SAE.

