To evaluate the clinical efficacy of GT0918 compared to placebo based on clinical status	
 
Proportion of subjects with all-cause hospitalization (defined as <math>\geq 24</math> hours) by Day 28
 
Proportion of subjects hospitalized (defined as <math>\geq 24</math> hours) due to COVID-19 related events by Day 28
 
Days of hospitalization due to all causes or COVID-19
 
Proportion of subjects with all-cause mortality by Day 28
 
Proportion of subjects with COVID-19 related mortality by Day 28
 
Proportion of subjects admitted to an ICU due to COVID-19 by Day 28
 
Days in intensive care unit (ICU)
 
Proportion of subjects requiring supplemental oxygen, high-flow oxygen, any ventilation or ECMO due to COVID-19 by Day 28
 
Proportion of subjects requiring mechanical ventilation or ECMO due to COVID-19 by Day 28
 
Days on supplemental oxygen/high flow oxygen devices/mechanical ventilation
 

Characterize the effect of GT0918 compared to placebo on symptom improvement or resolution	
Symptom Improvement:
 
 
Change in symptom score (total of ratings) from baseline to Days 3, 7, 14 and 28
 
Time to symptom improvement
 
Proportion of subjects demonstrating symptom improvement via the symptom questionnaire (total of ratings) on Days 3, 7, 14 and 28
 
 
Symptom resolution:
 
 
Proportion of subjects demonstrating symptom resolution via the symptom questionnaire on Days 3, 7, 14 and 28
 
Time to symptom resolution
 

Characterize the effect of GT0918 compared to placebo on SARS-CoV-2 viral load clearance	
 
Change from baseline to Days 3, 7, 14 and 28 in SARS-CoV-2 viral load
 
Proportion of subjects that achieve SARS-CoV-2 clearance (Days 3, 7, 14 and 28)
 
Time to SARS-CoV-2 clearance
 
SARS-CoV-2 viral load area under the concentration-time curve (AUC) assessed to days 3, 7, 14 and 28
 

Characterize the effect of GT0918 compared to placebo on safety	Safety assessments such as AEs, SAEs and laboratory data
Exploratory	Exploratory

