#### **10.8 Interim Analysis**

An interim analysis will be conducted when 334 subjects completed Day 28 after first dose. The objective of the interim analysis to assess safety, futility, efficacy, sample size adjustment as well as potential enrichment of the population to enroll a population at higher risk for an infection requiring hospitalization or oxygen support in case the observed rates for the primary endpoint in the control arm are lower than expected. An independent data monitoring committee (IDMC) will review the unblinded interim analysis report to assess the objectives of the interim analysis and provide recommendations about early study closure, change study population, or change to study sample size. Rigorous steps will be taken (e.g., firewalls) where possible to minimize the information that can be inferred by observers.

The futility criterion for the study will be based on the conditional power of the study being <10%. The efficacy criterion will be based on the one-sided p-value of the primary endpoint analysis as <0.0015. In this case the stopping boundary for efficacy is met and the study could be stopped for efficacy.

The topline safety analysis will include treatment related SAE including death. The IDMC can recommend stopping the study.

The conditional power will be evaluated based on primary endpoint in the interim analysis. IDMC could recommend a change of the subject population to enroll more subjects if the event rate is lower than expected. The IDMC will review the interim efficacy results and in case of substantial treatment differences between subpopulations, e.g., <50 years compared to  $\geq$ 50 years, provide recommendations for modifications of further enrollment. Criteria for those recommendations will be defined in the DMC charter. The consequences of those recommendations on the statistical analysis as well as the samples size adjustment will be summarized in a separate document and attached to the statistical analysis plan.

If the conditional power of the study at the time interim analysis is between 50% to 80% (promising zone approach), the sample size could be increased to a maximum of 1500 subjects based on the

efficacy in the interim analysis for overall population. If the conditional power of the study is above 80% power the sample size will not be changed. The detailed exact rule for sample size re-estimation will be pre-specified in the DMC charter.

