4.11.3 Deaths, Serious Adverse Events, and Other Significant Adverse Events

SAE

An SAE is defined as one of the following:

- Is fatal
- Is life-threatening
- Results inpatient hospitalization or prolongation of existing hospitalization
- Results in a persistent or significant disability/incapacity
- Constitutes a congenital anomaly/birth defect
- Is medically significant, i.e., defined as an event that jeopardizes the patient or may require medical or surgical intervention to prevent one of the outcomes listed above
- Note that hospitalizations for the following reasons should not be reported as SAEs:
 - Routine treatment or monitoring of the studied indication, not associated with any deterioration in condition.
 - Elective or pre-planned treatment for a pre-existing condition that is unrelated to the indication under study and has not worsened since signing the informed consent.

- Social reasons and respite care in the absence of any deterioration in the patient's general condition.
- Note that treatment on an emergency outpatient basis that does not result in hospital admission and involves an event not fulfilling any of the definitions of a SAE given above is not an SAE.

AE Summaries by System Organ Class and Preferred Term

The incidence for the following will be summarized by SOC and PT, unless otherwise specify:

- SAEs
- SAEs Related to Study Drug
- SAEs with Outcome Fatal
- TEAEs Leading to Study Drug Discontinuation

Separate tables for on-treatment period and safety follow up period will be provided, and below by-subject listings will be provided:

- All SAEs
- All Fatal SAEs
- All AEs leading to Study Drug Discontinuation

Adverse Events of Special Interest (AESI)

Adverse events of special interest to be monitored include gastrointestinal, cardiovascular, hepatic, and neurological adverse events (dizziness, headache), hematological (anemia, leukopenia, neutropenia) and elevated creatinine kinase. (Appendix 6.5)

TEAEs of special interest will be summarized by SOC and PT.

Time to TEAEs of Special Interest

Time to TEAEs of special interest (in days) is defined as:

First date when TEAEs of special interest onset - first dosing date + 1.

If a patient has not experienced TEAEs of special interest by completion or early discontinuation of study/study treatment, the patient will be censored at the date of their last visit.

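### COVID-19 deaths and hospitalizations handled as expected progression enter no AE/SAE table; on D29-D42 such deaths can show only as a disposition reason and such hospitalizations only in a listing

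*Protocol*

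**What the plan says.** Protocol 8.1.2 lists events that are not adverse events. COVID-19 hypoxemia needing oxygen or ventilatory support, and COVID-19 respiratory failure, are "exempt from AE reporting unless the investigator deems the event to be related to the administration of study drug". A further item removes "The disease/disorder being studied or expected progression, signs, or symptoms of the disease/disorder being studied, unless more severe than expected" for the subject's condition.

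Protocol 8.3.1 makes AE status a precondition for SAE status: "If an event is not an AE per definition above, then it cannot be an SAE even if serious conditions are met". Its own examples are "hospitalization for signs/symptoms of the disease under study, death due to progression of disease".

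Protocol 8.1.1 says that "clinical sequelae resulting from lack of efficacy will be reported as AE or SAE if they fulfill the definition of an AE or SAE".

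In the SAP safety section, deaths appear as "SAEs with Outcome Fatal" (4.11.2 and 4.11.3), as Grade 5 TEAEs, and under the Died category of TEAE severity (4.11.2). The AE overview in Protocol 10.7.2 counts deaths due to an AE.

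Protocol Section 3 lists as a secondary endpoint "Proportion of subjects with all-cause mortality by Day 28". The current SAP endpoint list (3.3.2) and secondary analyses (4.10.3) contain no mortality endpoint, and Protocol 10.1 gives the SAP precedence where the two differ.

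For the interim, Protocol 10.8 says "The topline safety analysis will include treatment related SAE including death".

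**The concern.** An ineffective or harmful drug could hurt these outpatients by making COVID-19 worse or longer. If that harm is classified as expected progression, it leaves the AE and SAE data by definition, and whether it is so classified rests on the judgment of a blinded investigator. The section of the SAP whose title begins with deaths would then have no table of deaths as such. A reader of the safety tables would see too few deaths, and the shortfall would differ by arm if progression differs by arm. The all-cause mortality endpoint that would have made up for this is no longer in the analysis plan. D29-D42 is a defined safety period (SAP 4.11), yet its tables are all AE-based, so the same exemption removes these events from them.

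**Working it through.** There is no planned figure to reproduce. The check follows one kind of event, a COVID-19 death or hospitalization handled as expected progression and so without an AE record, through each SAP output that could show it.

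| SAP output | Death by Day 28 | Death D29-D42 | Hospitalization D29-D42 |
|---|---|---|---|
| Fatal SAE rows and tables (4.11.2, 4.11.3) | No | No | Not applicable |
| Grade 5 and Died TEAE rows (4.11.2) | No | No | Not applicable |
| Other AE and SAE tables, including those for safety follow-up (4.11.2, 4.11.3) | No | No | No |
| Component summary of the primary endpoint (4.10.2) | Yes | No, stops at Day 28 | No, stops at Day 28 |
| NIAID scale, category 1 for death (4.10.3) | Yes | No, last time point Day 28 | No, last time point Day 28 |
| Hospitalization summary and time to hospitalization (4.10.3) | Not applicable | Not applicable | No, stops at Day 28 |
| Listing of hospitalization events (4.10.3) | Not applicable | Not applicable | Possible, no Day 28 limit stated |
| Disposition (4.4.1) | Possible, as a reason | Possible, as a reason | No |

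The disposition entry follows from two places. SAP 4.4.1 tabulates the number of and reasons for early withdrawal from the study, and Protocol 7.1.7 includes death among the reasons for ending follow-up. The table has no cause of death and does not separate D29-D42 from the rest.

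Uncovered period: 42 - 28 = 14 days, and 14/42 = 33% of study days. This is calendar time. It is not a share of the risk, which is likely to be concentrated earlier.

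AE definitions: 8.1.1 asks for sequelae of lack of efficacy to be reported if they meet the definition, 8.1.2 narrows that definition, and 8.3.1 names death from progression as an event that cannot be an SAE. SAP 4.11.3 repeats the SAE criteria, including a fatal outcome, without the restriction in 8.3.1. Two sites could report the same death differently while each following the text.

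**The case against.** The strongest reply is that worsening COVID-19 is the primary endpoint, so it is measured as efficacy and is not hidden. Protocol 8.1.1 says as much about lack of efficacy. This stands through Day 28: deaths are in the component summary and in NIAID category 1, and all-cause hospitalization is tabulated. Treating missing assessments as success does not erase a recorded death, and Protocol 7.1.5 provides for a search for vital status. The mITT and Safety Sets both require at least one dose, so they differ little. The protocol's mortality endpoint also stops at Day 28, so a Day 42 table is an addition to what the protocol lists.

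A reader might infer more than the documents support:

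- That COVID-19 deaths can never be SAEs. Protocol 8.1.2 keeps events judged drug-related and, for progression, events more severe than expected.
- That the protocol flatly contradicts itself. Section 8.1.1 is conditional on the definition. The text is unclear and needs reconciling, but it can be read consistently.
- That deaths on D29-D42 are in no table at all. Disposition can show them, and deaths that do have an SAE record enter the follow-up SAE tables.
- That the IDMC sees only treatment-related events. Protocol 10.8 says what the topline analysis will include, not that it is limited to this. The IDMC also reviews the unblinded primary endpoint, and under Protocol 4.2 it monitors AEs, SAEs and laboratory data. The charter is not available.
- That several deaths would be missed. Applying the 1-2% control mortality of the Brazilian study to 334 placebo subjects gives 334 x 0.01 = 3.3 to 334 x 0.02 = 6.7. Hospitalization in those control groups was 19-27%, whereas SAP 4.10.1.1.3 reports less than 2% here. If deaths per hospitalization were the same (an assumption) and the placebo rate were 2%, the result is 334 x 0.02 x 2/27 = 0.5 or 334 x 0.02 x 1/19 = 0.35.
- That comparison with the Brazilian study is lost. Its placebo SAE rates (27% in men, 19% in women) equal its hospitalization rates, and hospitalization is still tabulated here.

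**Conclusion.** The concern holds in a limited form. A COVID-19 death or hospitalization handled as expected progression is in no AE/SAE table of the SAP, because every such row needs an AE record. Deaths by Day 28 remain visible in efficacy outputs. For the last 14 of 42 days there is no mortality, efficacy or AE/SAE summary of these events; a death can appear only as a disposition reason and a hospitalization only in a listing. The missing Day 28 all-cause mortality endpoint is a plain difference between the protocol and the SAP. The SAP revision history records the removal of mortality analyses, but the point rests on the current text.

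The gap is in reporting and does not affect the primary test. With hospitalization below 2%, few deaths are to be expected, and no count of missed deaths is claimed. With so few, however, omitting even one could change how the safety table reads. The conclusion assumes that sites apply Protocol 8.1.2 and 8.3.1 as written. The eCRF and IDMC charter were not available.

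**What to change.** - SAP 4.11.3: add by-arm tables and listings on the Safety Set of all deaths from any cause, by Day 28 and through Day 42, and of all hospitalizations of at least 24 hours through Day 42. Include events whether or not they were reported as AE or SAE, and give the cause.
- SAP 3.3.2 and 4.10.3: restore all-cause mortality by Day 28, as in Protocol Section 3.
- Protocol 10.8: state that the interim safety summary shows all deaths and all SAEs by arm, not only treatment-related ones.
- Protocol 8.1.1, 8.1.2 and 8.3.1: reconcile the text so that sites classify the same event in the same way. The new tables are needed whichever way this is settled.

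The cost is a few tables. Vital status is already sought (Protocol 7.1.5), hospitalization events are recorded, and a Day 42 call is scheduled. One point to confirm is that the hospitalization eCRF page stays open to Day 42, since Protocol 7.2.1.1 describes collection of the composite events by Day 28. Expedited reporting rules need not change for the tables to be added.
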